Collectively, these data highlight several important points: 1) recurrent hypoglycemia can result in unawareness, with episodes possibly more frequent than appreciated by patients, leading to clandestine damage; 2) hypoglycemia can directly result in cell damage or death, neuroinflammation, and a pro-thrombotic state; 3) hypoglycemia in patients with diabetes has been shown to have serious and detrimental cognitive consequences, both for short-term patient safety and long-term cognition; 4) it is possible that patients undergoing bariatric surgery may have a pre-existing neural vulnerability due to prior history of obesity, with subsequent hypoglycemic insults; 5) understanding the impact of recurrent hypoglycemia on cognition in this understudied group is essential for risk assessment, raising provider awareness, developing more effective patient teaching strategies, and informing treatment, to help avoid potential cognitive decline.

In this study, we will assess and compare cognitive function in patients with hypoglycemia without a history of diabetes, as well as in RYGB patients with and without PBH. We will also assess and compare depressive symptoms between groups, and their potential relationship to cognition.

III. Study Design

a. Recruitment Methods

Participants will be recruited into 4 groups: (1) patients with hypoglycemia after upper gastrointestinal surgery, recruited from the Joslin Hypoglycemia Clinic, (2) asymptomatic post-bariatric patients, recruited from postoperative surgical clinics at Brigham and Women's Hospital, (3) patients with hypoglycemia and no history of upper gastrointestinal surgery, and NO current diagnosis of diabetes or pre-diabetes, recruited from the Joslin Hypoglycemia Clinic, (4) participants without hypoglycemia or upper gastrointestinal surgery (controls), recruited by local advertisement. Some participants may be recruited from other hypoglycemia studies at Joslin.

The Joslin Hypoglycemia Clinic has emerged as a referral clinic for patients with hypoglycemia from around the country, and particularly the New England region. Over 300 individuals have been evaluated in this clinic since its inception, and new patient referrals continue to increase as the awareness of hypoglycemia is increasing among patients and physicians alike. Thus, we have immediate access to a large pool of highly motivated patients.

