There will be no involvement of special vulnerable populations such as fetuses, neonates, pregnant women, children, prisoners, institutionalized or incarcerated individuals, or others who may be considered vulnerable populations.

Please note that duration of hypoglycemia will not be included in either inclusion or exclusion criteria, but will be included as a covariate in our analyses.

c. Number of Subjects

Participants will be recruited into 4 groups, (1) patients with PBH, recruited from the Joslin Hypoglycemia Clinic, (2) asymptomatic post-RYGB patients, recruited by advertisement flyers at postoperative surgical clinics at local hospitals (e.g. Brigham and Women's and Beth Israel Deaconess Hospitals), (3) patients with hypoglycemia and no history of upper gastrointestinal surgery, and NO current diagnosis of diabetes or pre-diabetes, recruited from the Joslin Hypoglycemia Clinic, (4) controls, recruited by local advertisement. We anticipate screen failure and drop out rate of 20% each. We plan to enroll patients with hypoglycemia continuously over the next 4 years. We anticipate performing cognitive testing in up to 20 participants in each of the four groups, based on availability of grant funding.

d. Study Timelines

The total duration of the study will be one to three weeks: one screening call and one study visit. We anticipate recruitment to continue for up to 4 years, concurrent with grant funding.

There is no plan in the current study to re-contact patients after the study has been completed.

e. Study Endpoints

Primary endpoints:

- Assessment of memory

Secondary endpoints:

- Assessment of executive function, language and psychomotor speed
- Assessment of depressive symptoms using the Beck Depression Inventory (BDI)
Analysis to assess the effects of participant group, and BDI scores (depressive symptoms), on standardized quantitative scores for each cognitive domain assessed (memory, executive function, language and psychomotor speed).

f. Study Procedures

An initial pre-screening phone call will occur with focus on inclusion, and exclusion criteria. The PHQ-2 will be administered as part of the screening process to assess for the presence, on a nearly daily basis, of both of the two cardinal symptoms of major depressive disorder. Individuals will be told that as part of the screening process they will be asked 2 questions about symptoms related to their mood. For individuals who

CHS Protocol Number	00000098		

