Protocol Version	4.0	Version Date	5/18/2021

are ineligible due to their PHQ-2 score, the study physician or nurse practitioner will offer to contact their primary care physician and recommend referral for mental health assessment. PHQ-2 forms completed via phone for those who are not eligible or who do not want to participate will be disposed of in a secure waste bin (for shredding) immediately after screening.

The study visit will then be scheduled for eligible participants. At this visit, we will test the hypothesis that hypoglycemia is associated with changes in cognitive function in the domains of memory, language, executive function, and psychomotor speed. Secondarily, we will also test the hypothesis that recurrent hypoglycemia is associate with higher scores on the BDI (depressive symptoms), and that BDI scores will be negatively correlated with cognitive function.

Sites: Participants will be recruited at Joslin Diabetes Center and via advertisement. All clinical evaluation will be performed on the clinical research unit of the Joslin Diabetes Center.

Study Visit: After informed consent, patients will undergo a history, and EKG, with emphasis on inclusion/exclusion criteria. Blood glucose will be assessed by capillary glucose. Prior to cognitive testing, participants will also be asked to complete the BDI, measuring depressive symptoms. Participants will be offered breaks of up to 10 minutes between components of the assessment.

Cognitive Testing: Prior to cognitive assessment, blood glucose levels will be assessed by capillary glucose testing. If glucose level is less than 70 mg/dL, glucose tablets and a snack will be provided, and glucose levels will be rechecked every 15 minutes until levels exceed 80 mg/dL. If during the course of testing a patient develops symptoms of hypoglycemia, blood glucose levels will be checked, and if needed, treated as above. Testing will not be resumed until glucose levels exceed 80 mg/dl.

The neuropsychological tests include:

a) Intelligence

The National Adult Reading Test (NART) is composed of a list of 50 words that progress in level of difficulty. The participant is instructed to read each word aloud while the examiner tracks the number of errors made. This test was designed in order to estimate premorbid intelligence based on the test taker's word familiarity.

b) Working Memory and Attention

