Data Collection and Storage: Research material for this study will consist of data obtained during the study visit, including medical history, and cognitive testing. Data will be recorded on case report forms, as well as cognitive testing forms, and stored in participant-specific binders. Data will be stored at the Joslin Diabetes Center in locked cabinets and rooms accessible only to study staff. All study participants will be assigned a unique study identifier. Publications or public presentations will not provide any information which could identify individual study participants or their families. Data analysis will commence once the entire cohort has been studied.

g. Data and Specimen Banking

After study completion, primary written materials (cognitive battery scoring and answer sheets) will be stored in locked filing cabinets accessible only to current study team members, and data will be stored on shared drives accessible only to current study team members approved by IRB. Identifiers will not be shared with anyone beyond the study team.

h. Data Management

Study Records Retention and Storage

Study documents will be retained for at least 10 years following study conclusion.

Each participant will be assigned a unique study ID acronym and number. Study data will be identified with this study ID, not with participant's names. Study documents will be stored in locked file cabinets or locked storage rooms and only authorized study staff will have access to these files. Electronic data will be stored on a password-protected network accessible only to authorized staff. Only deidentified information will be transferred between sites. All data transfer between study sites will be performed via secure encrypted file transfer (e.g. Movelt).

Data Monitoring

Designated personnel from the study site will be responsible for maintaining quality assurance (QA) and quality control (QC) systems to ensure that the study is conducted, and data are generated, documented, and reported, in compliance with the protocol, Good Clinical Practice (GCP), and the applicable regulatory requirements. Adverse events will be prioritized for monitoring.

Analysis plan for the primary study endpoints

- (1) The distributions of relevant variables will be examined for outliers and to determine appropriate statistics for use. χ^2 , Kruskal-Wallis, and ANOVA tests will be used to examine categorical differences.

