- (2) ANOVA tests will be used to assess the effects of group standardized quantitative score on each of the assessed cognitive domains.
- (3) Cohen's delta (d) may be used to assess effect size between groups

CHS Protocol Number	00000098		
Protocol Version	4.0	Version Date	5/18/2021

Sample size and power.

Since the cognitive assessments represent a pilot study, and no data are available in a similar population to guide power analysis, our sample size is guided by anticipated feasibility of recruitment.

i. Confidentiality

Representatives of the IRB or authorized representatives from Joslin Diabetes Center, and the NIH may inspect all documents and records required to be maintained by the investigator, including but not limited to, medical records (office, clinic, or hospital) for the participants in this study. The clinical study team will permit access to such records.

The study participant's contact information will be securely stored at each clinical site for internal use during the study. At the end of the study, all records will continue to be kept in a secure location for as long a period as dictated by local IRB and Institutional regulations.

j. Provisions to Monitor the Data to Ensure the Safety of Subjects

Data safety and monitoring plan. This plan will be implemented and strictly followed. The PI will be responsible for ensuring that recruitment and phenotypic analyses are conducted in accordance with the IRB-approved protocol and will review all adverse events and serious adverse events. The Joslin PI will also perform a periodic review of all data from phenotypic analyses. The members of the study team will conduct regularly scheduled meeting approximately weekly as well as on an as-needed basis to review status of the study inclusive of enrollment, oversight of informed consent, general conduct of the study as well as reporting of any complications as needed to the IRB. Safety data (including AE/SAE logs and protocol deviations) will be collected and reviewed every 3 months or as needed.

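### Item (2) of the primary analysis plan reads as a group-only ANOVA of four non-randomised groups; NART has no analytic role, and the promised duration covariate is missing from the plan and unsuitable for this comparison

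*Combined protocol and SAP*

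**What the plan says.** The analysis plan is in section III.h, under the heading for the primary study endpoints, and has three items.

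- Item (1): "The distributions of relevant variables will be examined for outliers and to determine appropriate statistics for use". It adds chi-square, Kruskal-Wallis and ANOVA tests for categorical differences. The variables are not named.
- Item (2): "ANOVA tests will be used to assess the effects of group standardized quantitative score on each of the assessed cognitive domains".
- Item (3): Cohen's d may be used for effect size between groups.

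None of the three names a covariate. Other sections bear on the same comparison:

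- III.b, closing note: "duration of hypoglycemia will not be included in either inclusion or exclusion criteria, but will be included as a covariate in our analyses".
- III.e, under the secondary endpoints: "Analysis to assess the effects of participant group, and BDI scores (depressive symptoms), on standardized quantitative scores for each cognitive domain assessed". Memory, the primary endpoint, is among the domains listed.
- III.f, on NART: "This test was designed in order to estimate premorbid intelligence". NART appears in no endpoint in III.e and in no item in III.h.
- III.a: groups 1 and 3 come from the Joslin Hypoglycemia Clinic and group 2 from postoperative surgical clinics. Group 4 consists of "participants without hypoglycemia or upper gastrointestinal surgery (controls), recruited by local advertisement". Research Match is a further source not tied to a group, and "Some participants may be recruited from other hypoglycemia studies at Joslin".

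Section III.j calls the study observational. Section III.c plans up to 20 participants per group.

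**The concern.** A referral clinic that draws patients from around the country, surgical clinics and local advertisement may bring in people with different education and prior ability. If they do, a group-only comparison of memory scores mixes that difference with any effect of hypoglycemia, and can either mimic or hide one. The battery already contains a test meant to measure prior ability, but the plan does not use it. The one covariate that the protocol does promise is not in the plan.

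This matters even in a pilot. Section I states two hypotheses about impairment and says the study should identify the cognitive domains to take into a larger sample. A domain could be carried forward or dropped because of who was recruited.

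**Working it through.** **1. Text comparison.**

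| Term | Promised or collected | In items (1)-(3) |
|---|---|---|
| Duration of hypoglycemia | III.b, as a covariate, with no limit to secondary analyses | No |
| BDI | III.e, under secondary endpoints | No |
| NART | III.f, in the battery | No |
| Age (18 to 70, III.b) | Known at screening | Only if the scores are age-normed; what standardized means is not stated |

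**2. Can duration do the adjusting?** Controls have no history of hypoglycemia and group 2 has no history of symptomatic hypoglycemia (III.b), so duration is zero or undefined in both. If zeros are entered, the model of four group means plus duration can be fitted (design rank 5 of 5). The slope, however, comes only from groups 1 and 3, and every contrast with groups 2 or 4 becomes an extrapolation to zero duration. Duration also carries no information on prior ability.

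**3. Can BDI do it?** Section III.f hypothesises that BDI rises with recurrent hypoglycemia. BDI may therefore lie on the path from exposure to cognition, and a BDI-adjusted group effect answers a different question.

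**4. Size of the exposure (illustration).** The plan gives no power calculation, alpha or SD, so there is no figure to reproduce. Assumed: two-sided alpha 0.05; both hypoglycemia groups lower on NART by a stated gap in SD; NART-memory correlation r; no true effect of hypoglycemia.

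The bias in the memory contrast is b = gap × r. With two groups against two, λ = n × 4 × (b/2)² = n × b². The rejection rate is the upper tail of a noncentral F(3, 4n − 4).

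| n per group | gap | r | b | λ | Rejection rate |
|---|---|---|---|---|---|
| 20 | 0.50 | 0.3 | 0.150 | 0.45 | 7.6% |
| 20 | 0.50 | 0.5 | 0.250 | 1.25 | 12.9% |
| 20 | 0.25 | 0.3 | 0.075 | 0.11 | 5.6% |
| 20 | 0.25 | 0.5 | 0.125 | 0.31 | 6.8% |
| 10 | 0.50 | 0.3 | 0.150 | 0.225 | 6.2% |
| 10 | 0.50 | 0.5 | 0.250 | 0.625 | 8.5% |

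In a simulation with 10,000 studies per setting (gaps 0 to 0.8 SD, r 0.3 to 0.6, n = 20), ANCOVA on the premorbid score rejected in 4.6% to 5.3%. With no gap, both models held about 5%.

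**5. What adjustment does to precision.** Residual degrees of freedom are 80 − 4 = 76 without covariates and 73 with NART, age and sex. Assume age and sex explain nothing. Relative to the unadjusted analysis, the expected variance of a pairwise difference is

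v = (1 − r²) × [1 + (3 + gap²/0.1)/72], where 0.1 = 2/20 and 72 = 76 − 3 − 1.

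- Gap 0, r = 0.3: v = 0.91 × (1 + 3/72) = 0.95.
- Gap 0, r = 0.5: v = 0.75 × (1 + 3/72) = 0.78.
- Gap 1, r = 0.3: v = 0.91 × (1 + 13/72) = 1.07.

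The pairwise difference detectable with 80% power is 0.90 SD unadjusted (76 df). With balanced groups and adjustment (73 df) it is about 0.87 SD for r = 0.3 and 0.79 SD for r = 0.5. With a 1 SD gap and r = 0.3, the variance is about 7% higher.

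**6. Over-adjustment.** If hypoglycemia itself lowered NART by an assumed 0.25 SD, adjustment would remove r × 0.25 = 0.075 to 0.125 SD of a real memory effect.

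**The case against.** - **The harm is hypothetical.** The gap, its direction, its two-against-two pattern and r are all assumed, and at the lower values the rejection rate barely exceeds 5%. The study is a feasibility-sized pilot with no stated error rate. This stands. A reader might infer that the groups do differ in ability or that the planned ANOVA is biased; the documents contain no data that support either.
- **The plan may not be group-only.** Item (2) may have lost words and never says unadjusted, and the III.b note can be read as supplementing it. In part this stands: group-only is the natural reading, not a certain one. It does not rescue the plan, since no section says where duration enters, and duration cannot correct contrasts with the groups that have no hypoglycemia.
- **BDI is not a contradiction.** A reader might infer that the group-plus-BDI analysis conflicts with item (2). It does not. It is listed under secondary endpoints, whereas items (1) to (3) are headed as the primary plan. It only lacks a written model.
- **NART may be examined under item (1).** It could be among the unnamed variables. Comparing NART between groups is still not adjustment.
- **Unadjusted analysis is defensible.** NART is a word-reading test taken after exposure. Section II reports impaired memory and language with recurrent hypoglycemia in type 1 diabetes, and the RAVLT tests verbal memory. Adjustment could therefore absorb a real effect on the primary endpoint. This stands, and is why the adjusted model should accompany the ANOVA and not replace it.
- **Covariate choice is partly judgement.** Section II names BMI and depression as related to cognition and does not mention sex. The visit procedures list no height or weight, though history and medical records might supply them, so whether BMI is available is unknown.

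**Conclusion.** The concern holds as an omission that should be fixed, with moderate confidence. The plan compares differently recruited, non-randomised groups with group as the only named factor, leaves NART unused, and does not place the duration covariate that section III.b promises. No bias is demonstrated. Under the assumptions stated, the false-positive rate at 20 per group ranges from near nominal (5.6%) to 12.9%. If the groups turn out balanced, there is no confounding by prior ability and adjustment brings a modest gain in precision. If they differ strongly, adjustment can cost some precision. The documents do not support going further and calling the adjusted result the right primary one.

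**What to change.** In section III.h:

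- Rewrite item (2) so that it is readable, and keep the unadjusted ANOVA of each domain score on group as the primary result.
- Add, for every domain, a prespecified ANCOVA on group, NART-estimated premorbid IQ, sex and age, reported beside the ANOVA. Omit age where the score is age-normed, and state how each score is standardized.
- Flag a domain whose group difference changes materially after adjustment as possibly due to recruitment differences, before it is carried forward or dropped.
- Tabulate NART, age and sex by group.
- Use duration of hypoglycemia only in analyses within the two hypoglycemia groups, and amend the closing note of III.b to match.
- Write out the BDI analysis of III.e as a separate secondary model.
- State as limitations that NART is measured after exposure and that confounding by other factors, such as BMI, may remain.

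The cost is wording. NART is already in the battery, and age and sex are known at screening. The adjusted model uses about 3 of 76 residual degrees of freedom. It may absorb part of a real effect on language or verbal memory, and showing the unadjusted result as primary keeps that visible.
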